The main study assessments will be performed at baseline prior to flexible dose titration and then at the end of the fixed dose drug continuation phase. This will include: (1) patient reported measures, (2) objective measures of sleep activity, (3) neurocognitive functioning (4) assessment of associated symptoms such as fatigue, mood, and (5) quality of life. Additional assessment of patient-reported measures will be performed after dose escalation and prior to the fixed dose drug continuation. Due to practice effects and other issues related to repeated measurement, neurocognitive data will only be collected pre- and post-treatment.

Sleep diaries will be completed continuously throughout the ~10 week study. Seven-day actigraphy will be completed at each dose escalation and during the first and last weeks of fixed dose drug continuation.

Additional assessments will be performed as per the standard of care. In this population, it is standard of care for MR Brain to be performed roughly every 8-16 weeks. Data on tumor status by imaging (e.g. stable disease, imaging progression, etc) will be recorded prior to study treatment and following study treatment to assess for tumor progression as a factor contributing to changes in patient-reported and clinician assessed outcome measures.

Adverse events will be assessed every 7 days during flexible dose titration (via telephone) and at the end of the fixed dose treatment. Adverse event data will be compared to that reported in patients with narcolepsy.⁵⁰

Open Label Safety Study of Solriamfetol to Promote Wakefulness and Improve Cognition and Quality of Life in
 Patients with Primary Gliomas
 Wake Forest Baptist Comprehensive Cancer Center
 WFBCCC 98418

2. Study-Related Activities

	Pre-Study ^a ^k	Baseline Visit V1 (D1)	Begin Flexible Dose Titration (D8+1 dy)	Flexible Dose D7 (D15+1 dy)	Flexible Dose D14 (D22+1 dy)	Fixed Dose Initiation Visit V2 ^k (D29+7 dys)	End of Treatment Visit V3 (D70+7 dys)	30 day Follow Up Visit V4 ^k
Informed consent	X							
Demographics	X							
Medical history	X							
Concurrent meds	X					X	X	
Physical exam ¹		X				X	X	X
Vital signs ^b	X ^c	X				X	X	X
CBC w/diff, platelets	X					X	X	X
Serum chemistry ^d	X					X	X	X
B-HCG ^e	X							
Electrocardiogram (EKG)		X				X		
Adverse event evaluation		X	X ^f	X ^f	X ^f	X	X	X
Epworth Sleepiness Scale (ESS)	X	X ^g	X ^g	X ^g	X ^g	X ^g	X ^g	
Sleep Measures: Sleep diary, Actigraphy ^h		X ⁱ	X	X	X	X	X	

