Adverse events will be assessed by telephone call completed on D8+1 day, D15+1 day, and D22+1 day. Patients will be assessed in clinic at D29+7 days. Patients who report a symptomatic dose-limiting toxicity will de-escalate treatment back to the highest previously tolerated dose and will be seen for V2.

6. Fixed Dose Drug Continuation

At the completion of the flexible dose titration, patients will be seen for a routine study visit (V2) or via telehealth visit to document adverse events at the completion of flexible dosing, review sleep diary and actigraphy, and complete V2 assessments. Data from this interim time point may be used to clarify the trajectory of improvement, decline, and no change in study assessments. Patients will then proceed with fixed dose treatment at 300 mg p.o. once daily or the maximum tolerated dose for that patient.

Fixed dose drug continuation will be continued for 6 weeks. Patients will complete a sleep diary for the first 7 and last 7 days of fixed dose treatment; actigraphy will be collected continuously. At the completion of fixed dose treatment, patients will be seen for V3 study assessments (Section 6.7).

7. 30 Day Follow Up

All patients will be followed for 30 days following the completion of treatment to assess for delayed toxicity. Adverse events will be recorded at this 30 day follow up visit. If the patient is unable to return for this visit, adverse events will be recorded by telephone or telehealth visit.

8. Study Assessments

Assessment of sleep, neuro-cognitive function, fatigue, mood and quality of life will be assessed at baseline (V1) and at the end of the fixed-dose drug continuation phase of the study (V3). Given that patient drop out could occur during the course of the study treatment, study assessments that are not subject to significant practice and/or repeated measure effects will also be assessed after the flexible dose titration period (V2).

The following assessments will be performed:

1. Patient-reported outcome measures (PROMs) for sleep:

Changes in patient-reported outcomes measures (PROMs) are pivotal to cancer control drug approval.

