 - ≥ Grade 2 central nervous system (CNS) ischemia will be considered a DLT
 - ≥ Grade 2 neurological toxicities that interfere with activities of daily living and do not resolve spontaneously with steroids, anticonvulsants, or electrolyte correction within 7 days will be considered a DLT
 - Symptomatic CNS hemorrhage of any grade will be considered a DLT
 - ≥ Grade 3 seizure only if the patient requires inpatient hospitalization for medical intervention. A breakthrough seizure that is managed with minor antiepileptic drug modification will not be considered a DLT. Contact the Study Chair for clarification as needed.
- **Grade 3 and 4 non-hematological, non-CNS toxicities** will be considered dose limiting with the following exceptions:
 - Grade 3 nausea, vomiting, or diarrhea without sufficient prophylaxis with a duration <3 days
 - Insomnia
 - Alopecia
 - Fatigue
 - Grade 3 hyperglycemia that is reversible and without clinical symptoms
 - Grade 3 electrolyte disturbances that are asymptomatic and reversible within 3 days, and do not re-occur upon continuing or re-initiation at the same dose
 - Grade 3 or 4 hypophosphatemia, unless considered clinically relevant
 - Grade 3 or 4 elevations in alkaline phosphatase
 - Grade 3 hypertension unless inpatient hospitalization is required
 - A subject's first episode of deep venous thrombosis (DVT) or pulmonary embolism will not require dose modification

For patients who have begun the fixed dose drug continuation phase and experience a new dose-limiting toxicity, the study medication will be held until the DLT has resolved. If the DLT resolves within 14 days, the patient may resume therapy at the prior dose level (1 dose level reduction). If an additional dose reduction is required, the study medication should be discontinued.

Dose escalation will proceed for each patient according to the following scheme:

Dose Level	Solriamfetol
+1	75 mg, p.o. once daily
+2	150 mg, p.o. once daily
+3	300 mg, p.o. once daily

For patients who experience a dose limiting toxicity, the study drug will be de-escalated to the last tolerated dose. For patients who experience a dose-limiting toxicity at dose level +1, treatment will be discontinued and the patient will not receive further treatment.

2. Other Agent(s)

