Appendix T – Telephone Script

Study Number: _____ PID: _____

Investigator: [name]. Date: ____/____/____

Hello, my name is {TBD - Project Coordinator} and I am calling on behalf of {Wake Forest Baptist Medical Center}. May I please speak with {SUBJECT'S NAME}?

I am going to ask you several questions about any side effects that you have experienced in the last week. When answering these questions, I would like for you to think only about symptoms that you have had over the last 1 week. We will focus on the period of time that you have been on the current dose of the solriamfetol drug that is a part of this study.

Over the last 1 week, have you had any side effects from solriamfetol (the study drug)? Yes No

Over the last 1 week, have you had any of the following symptoms (and if so, please describe them)?

- Headache _____
- Nausea _____
- Decreased appetite _____
- Anxiety _____
- Diarrhea _____
- Dry mouth _____
- Insomnia _____
- Chest pain _____
- New shortness of breath _____
- Other _____

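### Adverse events are checked weekly in titration, but no contact is scheduled for about six weeks of fixed dosing, so ascertainment of the primary outcome differs by dose

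*Combined protocol and SAP*

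**What the plan says.** Section 7.1 states: "Adverse events will be assessed every 7 days during flexible dose titration (via telephone) and at the end of the fixed dose treatment". Section 7.5 names the calls: "Adverse events will be assessed by telephone call completed on D8+1 day, D15+1 day, and D22+1 day". It lists none after D22.

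The activities table in 7.2 marks adverse event evaluation at the baseline visit, at D8, D15 and D22, and then at two columns headed "Fixed Dose Initiation Visit V2 ^k (D29+7 dys") and "End of Treatment Visit V3 (D70+7 dys"), followed by the 30-day visit. It has no column between V2 and V3. Section 7.6 gives the purpose of V2 as to "document adverse events at the completion of flexible dosing", so V2 closes titration. The same section says: "Fixed dose drug continuation will be continued for 6 weeks".

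Section 7.9.1 has a rule for a new DLT in the fixed-dose phase. Drug is held, and then: "If the DLT resolves within 14 days, the patient may resume therapy at the prior dose level (1 dose level reduction").

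Two instruments bear on what happens between visits. The Appendix G diary has 42 daily rows and a side-effects column, but no section dates a review of it before V3. The Appendix T telephone script tells the patient: "I would like for you to think only about symptoms that you have had over the last 1 week". It adds that the focus is the time on the current dose.

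**The concern.** The primary hypothesis (Section 2.1) includes that serious events, such as confusion and seizures, are not more common at 300 mg than at 75 or 150 mg. Section 13.1 tabulates and tests adverse events by dose, and it does not mention length of exposure or frequency of assessment. The 75 mg and 150 mg weeks are each closed by a call after 7 days. The 300 mg titration week is closed by V2, but most time at 300 mg is closed by one visit about six weeks later. A dose comparison then mixes the effect of dose with differences in how long patients were exposed and how often they were asked.

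There is also a safety side. The 7.9.1 rule presumes that a fixed-phase DLT becomes known while the patient is still on treatment. The first scheduled evaluation after V2 is the end-of-treatment visit, when holding and resuming drug no longer has practical effect. Section 1.6 cites seizure risk and drug-induced cognitive dysfunction in this population as reasons to establish safety first. Those reasons apply to the long phase as much as to titration.

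**Working it through.** **Inputs**

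- AE evaluations during treatment: D8, D15, D22, V2 at D29 (+7), V3 at D70 (+7) (7.2 and 7.5).
- Fixed-dose phase: 6 weeks (7.6); 42 diary rows (Appendix G).
- Expected numbers: at least 30 patients reach 300 mg (13.4).
- Titration: 7 days at each dose (7.1).

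**Step 1. Reproduce the stated duration.** D29 to D70 inclusive is 70 − 29 + 1 = 42 days, and 42 / 7 = 6 weeks. This agrees with 7.6 and Appendix G. One sentence of 7.1 gives 8 weeks for the same phase. That inconsistency needs reconciling, and the figures below use the study days in the table.

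**Step 2. Interval between scheduled AE evaluations.**

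| Interval | Calculation | Days |
|---|---|---|
| 75 mg week | 15 − 8 | 7 |
| 150 mg week | 22 − 15 | 7 |
| First 300 mg week, nominal | 29 − 22 | 7 |
| V2 to V3, nominal | 70 − 29 | 41 |
| V2 to V3, late V2 and earliest V3 | 70 − 36 | 34 |
| V2 to V3, earliest V2 and late V3 | 77 − 29 | 48 |

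No contact is scheduled inside the V2 to V3 interval.

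**Step 3. Share of 300 mg exposure in the sparsely checked phase.** Assume that exactly 30 patients reach 300 mg and all complete the study at that dose without interruption.

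- Titration at 300 mg: 30 × 7 = 210 patient-days.
- Fixed phase at 300 mg: 30 × 42 = 1,260 patient-days.
- Share: 1,260 / (210 + 1,260) = 1,260 / 1,470 = 86%.

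The share does not depend on the number 30, because each completer contributes 42 / 49. Dropout or dose reduction during the fixed phase would lower it.

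**Step 4. Compare the schedule with the DLT rule.** V2 documents titration and V3 ends treatment. No scheduled evaluation lies between them, so none can detect a new fixed-phase DLT before treatment ends. Detection rests on spontaneous report, routine oncology care or hospitalisation.

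**Step 5. Look for anything that fills the gap.** The interim safety analysis in 13.7 follows completion of dose escalation. Appendix D requires reporting of unexpected grade 4 events, unplanned inpatient stays over 24 hours and deaths. It adds no contacts. Sleep diaries and actigraphy are not AE assessments.

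**The case against.** The strongest reply is that the practical loss may be small.

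- **Front-loading.** In the OSA randomized-withdrawal study described in 1.5.2, adverse events ran at 48.9% in titration and 10.2% in the stable-dose phase. Weekly calls match the escalation decisions. This stands and limits the size of the point. However, that stable phase lasted two weeks, against six here, in a different population.
- **The DLT rule is event-driven.** Most DLT criteria in 7.9.1 describe serious events that would often bring a patient to care without a call. Laboratory DLTs would not be found by telephone, and no blood tests are scheduled between V2 and V3. Both points stand.
- **The diary.** Appendix G lets patients note side effects daily, and Section 8 uses the diaries to track dose modifications. So transient events need not be lost. What remains is that no review date is set before V3.

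A reader might also infer four stronger things that the documents do not support.

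1. *That sparse checking biases the comparison in favour of 300 mg.* Section 13.1 analyses proportions of subjects. About seven weeks at 300 mg against one week at each lower dose raises that proportion, while sparse checking lowers it. The net direction is unknown.
2. *That a DLT starting in the first 28 of 42 days (67%) misses the 14-day window.* The 14 days in 7.9.1 concern resolution after drug is held. They are not a limit on detection counted from onset.
3. *That 83% of the fixed phase, (42 − 7) / 42, is never asked about.* This would require V3 to use the one-week recall of Appendix T. The documents specify calls only on D8, D15 and D22 and do not state V3's recall period.
4. *That V3 is an unprompted look.* The documents do not say how V3 elicits events. The visit includes an AE evaluation, physical examination, vital signs, blood tests and a medication review.

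**Conclusion.** The schedule gap is certain: 7.1, 7.2 and 7.5 agree, and no other section closes it. It is nominally 41 days (34 to 48), compared with 7 in titration, and covers the longest exposure at 300 mg or the patient's maximum tolerated dose. About 86% of patient-days at 300 mg lie in it, under the completion assumption in step 3. Scheduled ascertainment of the primary outcome therefore differs by dose, and the by-dose comparison in 13.1 is hard to interpret in either direction. The fixed-phase DLT passage and the monitoring schedule do not fit together and must be reconciled. Nothing here shows that many events would be missed, or that a DLT would go unnoticed. This is a cheap improvement and does not invalidate the design.

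**What to change.** - **Sections 7.1, 7.2 and 7.6.** Add AE telephone calls in the fixed-dose phase, using the Appendix T script, at regular intervals counted from the actual V2 date until V3. Every two weeks is one example; the protocol team sets the interval. Counting from V2 matters. Calls fixed at D43 and D57 would leave 77 − 57 = 20 days to a late V3, and with V2 on D36 the first call would come after only 43 − 36 = 7 days.
- **Recall period.** At these calls and at V3, ask about symptoms since the last contact.
- **Diary.** Review Appendix G at each contact and enter side effects in the AE log with onset date and dose at onset. The form prints only a 300 mg box, so dose at onset needs recording for patients on a lower dose.
- **Section 13.1.** Tabulate adverse events by dose separately for the titration week and the fixed-dose phase.
- **Section 7.9.1.** Reconcile the fixed-phase DLT passage with the monitoring schedule. No clinical rule is proposed here.

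**Cost.** A protocol amendment and, at two-week intervals, 2 to 3 short calls per patient: 36 × 2 = 72 to 36 × 3 = 108 in total, by existing staff. The third call arises only when V3 falls more than 42 days after V2. Observed AE counts at the maximum dose may rise.

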The table below outlines the assessment measures that will be used to evaluate attention, concentration, information processing speed, learning/memory, and aspects of higher-order executive functions. These measures were selected in accordance with previously established standards for cognitive assessment with brain tumor patients and many are used in our own multidisciplinary clinic.⁵⁴⁻⁵⁶ The protocol was modified slightly based on the skills most commonly identified as problematic for patients struggling with sleep disturbance and fatigue (attention/concentration and processing speed).

All proposed measures have adequate psychometric properties and most have been utilized in large national and international clinical oncology trials.^{57,58} Alternate forms of the measures will be used to reduce practice effects where possible though some measures are less sensitive to such effects and do not have alternate forms (Digit Span, Letter Number Sequencing, etc.).

Neuropsychological changes will be assessed on an individual basis though a reliability change index (RCI) can also be obtained to allow an objective measure of change in the measured skill.

The following measures will be used:

Test Name:	Skill Measured:	Alternate Versions:	Time to Administer:
Digit Span (DS)	Basic rote attention span	NA	5-10 minutes
Letter Number Sequencing (LNS)	Complex working memory	NA	5-10 minutes
Matrix Reasoning (MR)	Visual abstract reasoning	NA	15-20 minutes
Symbol Search (SS)	Speeded symbol discrimination	NA	2-3 minutes
Coding (CD)	Clerical speed and accuracy	NA	2-3 minutes
Controlled Oral Word Association Test (COWAT)	Lexical and semantic verbal fluency and executive control	2 forms	6 minutes
Trail Making Test Parts A and B (TMT A & B)	Attention, processing speed, and cognitive set shifting	NA	6 minutes
Montreal Cognitive Assessment (MoCA)	Global cognitive functioning	3 forms	15 minutes
Total			50 – 65 minutes

This battery will be completed at V1 and V3 only (see 7.2 Study-Related Activities). This will not be performed at the interim V2 time point due to concern with practice effects and limited alternate forms for many of these assessments.

4. Patient-Reported Associated Symptoms:

Sleep disturbances co-occur with symptoms of fatigue and impaired mood in patients with brain tumors. Furthermore, improvement in any one of these symptom domains can have downstream effects on the other.

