To assess fatigue, the Brief Fatigue Inventory (BFI) and Cancer Fatigue Scale (CFS) will be used (Appendix J & K). The BFI is a 9 item self-administered patient-reported questionnaire exploring the severity of fatigue and interference on life over the past 24 hours.⁵⁹⁻⁶¹ The Cancer Fatigue Scale is a 15-item self-administered patient-reported questionnaire exploring both overall and domain specific fatigue in cancer patients. The instrument explores three fatigue domains: physical effects of fatigue, cognitive effects, and affective issues related to cancer fatigue.⁶² The combination of these instruments provides both a unidimensional (BFI) and multidimensional (CFS) assessment of fatigue. The CFS domains will allow us to also explore whether there might be differential effects on physical fatigue or cognitive aspects of fatigue compared to the affective factors. The BFI and CFS have robust psychometric properties, have been validated in cancer patients, and were recently reviewed in the American Society of Clinical Oncology Patient-Reported Outcomes (PRO) Recommendations.^{42,43,60}

To assess depression, the Beck's Depression Inventory will be used (Appendix L). The BDI is a commonly employed measure of depressive symptoms and has been validated in cancer patients.^{63,64} A cutoff of BDI \geq 10 is often employed.⁶⁵

These measures will be completed at V1, V2, and V3 (see 7.2 Study-Related Activities).

5. Quality of Life:

The Functional Assessment of Cancer Therapy (FACT) questionnaires are commonly used to assess cancer-related quality of life (Appendix N). The FACT-Brain (FACT-Br) provides an additional set of disease-specific questions pertaining to brain neoplasms and is commonly used in brain tumor studies to evaluate disease-specific quality of life.⁶⁵

The FACT-Br will be assessed at V1, V2, V3 (see 7.2 Study-Related Activities).

9. Treatment Administration

Treatment will be administered on an outpatient basis. The study drug is to be taken orally once daily at approximately the same time each day. Each dose administered is to be recorded in the drug diary (Appendix F-G).

Reported adverse events and potential risks are described in Section 10.0. Appropriate dose modifications for are described in Section 8.0.

1. Definition of Dose-Limiting Toxicity (DLT)

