In the absence of treatment delays due to adverse events, treatment may continue for the duration of the study treatment (D70 +7 days) or until one of the following criteria applies:

- Disease progression requiring surgery or radiation therapy,
- Intercurrent illness that prevents further administration of treatment,
- Unacceptable adverse event(s),
- Patient decides to withdraw from the study, or
- General or specific changes in the patient's condition render the patient unacceptable for further treatment in the judgment of the investigator.

12. Duration of Follow Up

Patients will be followed for a minimum of 30 days after the last study drug is administered for adverse events monitoring.

13. Determination of Evaluable Patients

Patients who enroll in the study but do not take a dose of the study medication will not be considered evaluable and will be replaced. In other words, patients who begin the pre-treatment baseline assessment and do not take the study medication will not be evaluable and will be replaced.

14. Criteria for Removal from Study

Patients will be removed from study when any of the criteria listed in section 5.4 applies.

8 Dosing Delays/Dose Modifications

During the flexible dose titration period of this study, dose modifications will be performed according to the Dose-Limiting Toxicity scheme outlined in Section 6.9.1.

During the fixed dose drug continuation period of this study, for patients who experience a new dose-limiting toxicity (see Section 6.9.1) treatment dose will be modified according to the following scheme:

Dose Level	Insert Agent Name Dose
+1	75 mg, p.o. once daily
+2	150 mg, p.o. once daily
+3	300 mg, p.o. once daily

All dose modifications will be recorded, tracked and monitored via a drug diary (Appendices F and G) throughout the duration of study treatment.

9 Measurement of Effect

Tumor response and survival outcomes will NOT be included as an endpoint in this study. MRI Brain is included to track evidence of clinically documented progressive disease which could contribute to changes in patient-reported and clinician assessed outcome measures (see Section 7.8).

10 Adverse Events List and Reporting Requirements

1. Adverse Event List for solriamfetol

In the 12-week placebo-controlled studies in patients with narcolepsy and OSA, in the overall population the most frequent ($\geq 5\%$) adverse events that also had a higher incidence with solriamfetol than with placebo were:

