____ / ____ / ____	28	Yes  No 	

Open Label Safety Study of Solriamfetol to Promote Wakefulness and Improve Cognition and Quality of Life in
 Patients with Primary Gliomas
 Wake Forest Baptist Comprehensive Cancer Center
 WFBCCC 98418

Dose: 300 mg 			Side effects (including unusual symptoms),
Date	Day of six-week schedule	Taken	
____/____/____	29	Yes  No 	
____/____/____	30	Yes  No 	
____/____/____	31	Yes  No 	
____/____/____	32	Yes  No 	
____/____/____	33	Yes  No 	
____/____/____	34	Yes  No 	
____/____/____	35	Yes  No 	
____/____/____	36	Yes  No 	
____/____/____	37	Yes  No 	
____/____/____	38	Yes  No 	
____/____/____	39	Yes  No 	
____/____/____	40	Yes  No 	
____/____/____	41	Yes  No 	
____/____/____	42	Yes  No 	

Was the full six weeks completed? Yes No

If No, was this due to side effects? Yes No

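### The plan does not require dosing to continue until V3, so a compliant end-of-treatment assessment can fall up to 7 days off drug, which matters most for cognition

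*Combined protocol and SAP*

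**What the plan says.** **Length of fixed dosing.** Section 7.6 states "Fixed dose drug continuation will be continued for 6 weeks". Footnote h to the Section 7.2 table places the last week of this phase at about D63 to D70. The Appendix G diary has rows for days 1 to 42 and ends by asking "Was the full six weeks completed".

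**Timing of V3.** Section 7.6 adds "At the completion of fixed dose treatment, patients will be seen for V3 study assessments". The Section 7.2 table gives V2 as D29 with 7 days' allowance and V3 as "End of Treatment Visit V3 (D70+7 dys". No section sets a longest interval between the last dose and V3.

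**Limit on treatment.** Section 7.11 says "treatment may continue for the duration of the study treatment (D70 +7 days", followed by a list of stopping criteria.

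**Measurements.** Section 7.1 says "neurocognitive data will only be collected pre- and post-treatment", and Section 7.8 repeats the point: "This battery will be completed at V1 and V3 only". ESS, PSQI, fatigue, mood and quality of life are also measured at V2.

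**Analysis.** Section 13.2 compares pre- and post-treatment scores by paired t or Wilcoxon signed rank tests. It has no rule on time since the last dose. Section 13.4 names V3 as the post-treatment point for ESS.

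**The concern.** The study rationale summary (Section 1.6) intends the endpoints to be measured after a long period of stable dosing. The secondary hypotheses (Section 2.2) concern treatment at each patient's maximal dose. A V3 some days after the last tablet measures something else, yet the plan would pool it with V3 values taken on drug.

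Cognition has the most at stake. It is named in the study title and has no V2 measurement, so an off-drug V3 score has no on-treatment substitute and cannot be replaced afterwards. The other scales have a V2 value, although that one comes at the end of titration and not after stable dosing. Section 13.4 also says that the study should supply effect-size estimates for a later randomized trial. If benefit fades off drug, those estimates would be too small.

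**Working it through.** **Inputs.** V2 on D29 to D36 and V3 on D70 to D77 (Section 7.2); 42 daily doses from V2 (Section 7.6, Appendix G). One sentence in Section 7.1 mentions 8 weeks for this phase. Section 7.6, the phase list in 7.1, the diary and the visit schedule all give six, so six is used here.

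**Reproducing the plan's target day.** Day of dose 42 = V2 day + 41. For V2 on D29 this is 29 + 41 = D70, which matches the V3 target.

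**Gap at V3.** Gap = V3 day − (V2 day + 41). With V3 on D77 the longest gap is 77 − (V2 day + 41):

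| V2 day | Day of dose 42 | Longest gap (days) |
|---|---|---|
| D29 | D70 | 7 |
| D30 | D71 | 6 |
| D31 | D72 | 5 |
| D32 | D73 | 4 |
| D33 | D74 | 3 |
| D34 | D75 | 2 |
| D35 | D76 | 1 |
| D36 | D77 | 0 |

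**What each instrument captures in the worst case** (last dose D70, V3 on D77):

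- Neurocognitive battery: performed wholly off drug.
- CFS (current state) and the BFI items on now and the past 24 hours: wholly off drug.
- BDI (past week counting the day of completion, D71 to D77): 7 of 7 days off drug.
- FACT-Br (past 7 days, D70 to D76 or D71 to D77): 6 or 7 of 7 days off drug.
- PSQI (past month): 7/30 = 23% off drug.
- ESS: asks about recent times without a fixed window, so it is less exposed.
- Actigraphy and diary from the last week of dosing: tied to dosing days, not affected.

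**Could the ESS conclusion turn on this?** The only withdrawal figure in the documents is from the OSA randomized-withdrawal study (Section 1.5.2). ESS rose by 4.5 points over 2 weeks in responders switched to placebo. Section 13.4 hypothesises a change of at least 6.3 and states that 5.4 gives 80% power against the placebo change of 3.8. Both of the following assume that the OSA figure carries over to glioma.

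- Full 4.5-point loss in every affected patient: (6.3 − 5.4)/4.5 = 0.20; 0.20 × 36 = 7.2, so 8 patients.
- Linear loss with a 7-day gap: 4.5 × 7/14 = 2.25 points; 0.9/2.25 = 0.40; 0.40 × 36 = 14.4, so 15 patients, all at the worst-case gap.

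Even then the mean change would only have come down to about 5.4, where the plan still claims 80% power.

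**Cognition, fatigue, mood and quality of life.** The documents give no off-drug figure, so no corresponding calculation is possible.

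**The case against.** The strongest reply is that the plan already points to an on-drug V3. V3 is called the end-of-treatment visit, and Sections 7.1 and 7.8 place the assessments at the end of the fixed-dose phase. The Section 7.11 limit equals the V3 window. Its permissive wording introduces a list of stopping criteria, so it can be read as saying that treatment goes on unless one of them applies. A site that follows both sentences of 7.6 strictly would hold V3 as dosing ends. If both visits are on target, or both slip equally, there is no gap. Appendix G is a recording form and not a dosing rule; it also prints only a 300 mg box.

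Much of this stands. The intention is probably an on-drug V3, and the 7-day gap needs V2 with no slip, V3 with the greatest slip and dosing that stops at 42. But D77 is also where dose 42 falls for a D36 start, so the 7.11 limit does not show that a D29 starter should go on past D70. Section 7.6, footnote h and the diary that the patient holds all point to stopping at six weeks. Two patients could be handled differently and both be compliant.

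It is also fair to object that harm is not shown. Section 1.6 describes fatigue, cognition, mood and quality of life as probably slower to respond, and nothing in the documents shows that they reverse within a week. That stands: dilution is plausible, not demonstrated.

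Finally, Section 7.9 says "Each dose administered is to be recorded in the drug diary (Appendix F-G", so days since the last dose can largely be derived. That would reveal an off-drug cognitive score but could not replace it, and a dose after day 42 has no printed row.

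**Conclusion.** The point holds as a gap in the dosing instruction, and it should be closed. For a patient whose V2 falls within its window, a compliant V3 can be 0 to 7 days off drug. The maximum falls by one day for each day that V2 slips. This rests on six weeks meaning 42 daily doses and on dosing stopping there, as 7.6 and the diary allow.

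The consequence is confined to secondary outcomes. It is greatest for the neurocognitive battery, then for CFS, BFI, BDI and FACT-Br. Its size for these cannot be determined from the documents.

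A reader might infer three stronger things that the documents do not support:

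- *That V3 will usually be off drug.* The windows show which schedules are permitted, not how many patients will follow each of them.
- *That the ESS result is compromised.* On the only withdrawal figure available, 8 of 36 patients would need to lose the full 4.5 points merely to bring the hypothesised change down to the plan's own 80% power point.
- *That the safety assessment is weakened.* Adverse events are followed through V3 and for 30 days after treatment, so the primary outcome is not affected.

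**What to change.** 1. In Sections 7.6 and 7.11, state that, unless a stopping criterion applies, daily dosing at the fixed dose continues through the day of V3, with six weeks as the minimum and D77 as the latest day.
2. Extend the Appendix G diary from day 42 to day 49.
3. Record the date of the last dose at V3, and report days since last dose descriptively alongside the secondary outcomes.

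An analysis that drops V3 values taken more than a day after the last dose is not advised. Once dosing runs to V3, it would mainly remove patients who stopped early, including those who stopped for toxicity, and that is an informative exclusion.

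**Cost.** One sentence in each of two sections, seven diary rows and one field at V3. Fixed-phase exposure would range from 42 days (D29 to D70, or D36 to D77) to 49 days (D29 to D77), so late visits need up to 7 extra days of tablets. Total time on drug, D8 to D77, is at most 77 − 8 + 1 = 70 days, which Section 7.11 already allows. The sample size and the stated power do not change.
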